4.1 Inclusion Criteria

- 1) Patients diagnosed with bilateral cataracts and scheduled to undergo bilateral cataract surgery
- 2) Must be able to understand and sign an informed consent from that has been approved by an Institutional Review Board
- 3) Patient is over the age of 18
- 4) Patient must agree to comply with visit schedule and other requirements of the study
- 5) Females who are not pregnant and are not lactating. Females who are post-menopausal or surgically sterilized.

If the answer to any of the inclusion criteria are NO, the subject is ineligible to continue study participation

4.2 Exclusion Criteria

- 1) Patients with several ocular surface disease as defined by central corneal staining with fluorescein and/or a tear film osmolarity of greater than 340 in either eye

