Main Inclusion and Exclusion Criteria	
Inclusion: Patients undergoing bilateral cataract surgery
 
Exclusion: Patients with severe ocular surface disease as defined by central corneal staining with fluorescein and/or a tear film osmolarity of greater than 340 in either eye

Study product, Dose, Route, Regimen	DEXYCU (dexamethasone intraocular suspension) 9%, administered as a single dose, intraocularly in the posterior chamber at the end of surgery. The dose is .005 mL of dexamethasone 9% (equivalent to 517 micrograms)
Duration of subjects participation	Patients scheduled to undergo bilateral cataract surgery will be screened and have dry eye testing. If enrolled in the study, patients will have dry eye testing at 1 week and 3 weeks after surgery.
Reference product	The control group will utilize a standard post-cataract surgery regimen of topical gatifloxacin and topical prednisolone acetate.

1 Introduction

Evaluation of intraoperative use of Dexycu on the Signs and Symptoms of Dry Eye is a clinical research protocol and the study will be conducted in accordance with the protocol, Good Clinical Practice Standards, and applicable regulatory requirements.

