1.6 Risk/Benefits

The following adverse events rates are derived from three clinical trials in which 339 patients received the 517 microgram dose of DEXYCU. The most commonly reported adverse reactions occurred in 5-15% of subjects and included increases in intraocular pressure, corneal edema, and iritis. Other ocular adverse reactions occurring in 1-5% of subjects included, corneal endothelial cell loss, blepharitis, eye pain, cystoid macular edema, dry eye, ocular inflammation, posterior capsular opacification, blurred vision, reduced visual acuity, vitreous floaters, foreign body sensation, photophobia, and vitreous detachment.

2 Study Objectives

The objective of this clinical research is to evaluate whether the signs and symptoms of dry eye after cataract surgery improve with the addition of a DEXYCU intraocular injection. Multiple studies have established that dry eye worsens after cataract surgery. There is also

a strong body of evidence that shows that dry eye is inflammatory. The objective of this study is to evaluate whether the intraocular use of steroid impacts dry eye.

3 Study Design

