3.1 General Design

- The type/design of the study:
 - Prospective randomized controlled trial
- A description of the measures taken to minimize/avoid bias:
 - Patients undergoing bilateral cataract surgery will be randomized to the DEXYCU group (standard postoperative cataract regimen + intraoperative DEXYCU) in one eye or the STANDARD group (standard postoperative cataract regimen). Randomization will be done after screening visit, prior to surgery on the first eye and will be done by coin flip. Standard cataract regimen to be used: topical prednisolone acetate 1% qid and topical gatifloxacin qid for 1 week, then tid for 1 week, then bid for 1 week.
- Expected duration of subject participation
 - 3 weeks after cataract surgery
 - Patients undergoing cataract surgery will have dry eye testing prior to surgery, 1 week after surgery, and 3 weeks after surgery
- A summary description of the sequence and duration of all trial periods including follow-up, if any
 - Patients undergoing cataract surgery will have dry eye testing prior to surgery, 1 week after surgery, and 3 weeks after surgery

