5.2 Treatment/Dosing Regimen

DEXYCU (dexamethasone intraocular suspension) 9%, administered as a single dose, intraocularly in the posterior chamber at the end of surgery. The dose is .005 mL of dexamethasone 9% (equivalent to 517 micrograms)

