5.3 Method for Assigning Subjects to Treatment/Dosing Groups

Patients undergoing bilateral cataract surgery will be randomized to the DEXYCU group (standard postoperative cataract regimen + intraoperative DEXYCU) in one eye or the STANDARD group (standard postoperative cataract regimen). Randomization will be done after screening visit, prior to surgery on the first eye and will be done by coin flip. Patients who are randomly assigned to the DEXYCU group will receive a sequentially numbered drug kit.

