5.5 Prior and Concomitant Therapy

All medications that subjects are taking prior to cataract surgery will be permitted. Subjects are also permitted to utilize artificial tears in addition to the therapeutic regimens. The use of artificial tears will be tracked by the study team.

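### Nothing in the entry criteria stops a known steroid pressure responder, or a patient with raised or uncontrolled pressure at screening, from being randomised to added intraocular steroid

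*Combined protocol and SAP*

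**What the plan says.** **Entry.** Section 4.2 has a single exclusion, applied to each eye: "Patients with several ocular surface disease as defined by central corneal staining with fluorescein and/or a tear film osmolarity of greater than 340". The Study Summary gives the same criterion, "Exclusion: Patients with severe ocular surface disease as defined by central corneal staining with fluorescein and/or a tear film osmolarity of greater than 340", which shows that the adjective in 4.2 is a misprint for severe. The five inclusion criteria in 4.1 cover bilateral cataract, consent, age, compliance with visits, and pregnancy or lactation. None concerns pressure, glaucoma or response to steroid. Section 5.5 adds: "All medications that subjects are taking prior to cataract surgery will be permitted".

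**Steroid given.** Section 5.2: "The dose is .005 mL of dexamethasone 9% (equivalent to 517 micrograms". Section 3.1 gives this in addition to the standard drops: "Standard cataract regimen to be used: topical prednisolone acetate 1% qid and topical gatifloxacin qid" for the first week, then three times daily and twice daily for one week each.

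**Known risk.** Section 1.6: "The most commonly reported adverse reactions occurred in 5-15% of subjects and included increases in intraocular pressure, corneal edema, and iritis". The source is described there: "The following adverse events rates are derived from three clinical trials in which 339 patients received the 517 microgram dose of DEXYCU".

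**Allocation and pressure checks.** Section 5.3: "Randomization will be done after screening visit, prior to surgery on the first eye and will be done by coin flip". Section 6 has pressure measured at screening and on days 1, 7 and 21. The only rule that uses a pressure value is in 4.4: a postoperative patient above 35 mm who needs extra medication for it leaves the study.

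**The concern.** The protocol names pressure increase as one of the commonest reactions to the study drug, then sets entry criteria that take no account of pressure. Read literally, three kinds of patient are eligible: one whose pressure is already known to rise on steroid, one with uncontrolled glaucoma or ocular hypertension, and one with a high reading on the day of screening.

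This is a patient-safety point. Both groups receive topical prednisolone, so the avoidable part is the added intraocular dose. Drops can be stopped if pressure rises, whereas a single dose placed at the end of surgery has already been given by the time any postoperative reading is taken. That dose serves a research question about dry eye, so a patient kept out of the trial loses no standard care.

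**Working it through.** The plan states no figure on this point, so there is none to reproduce. The check sets the provisions side by side and then gives the scale.

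**1. Can any provision act before the dose?**

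| Provision | When it acts | Does it bar a patient at pressure risk? |
|---|---|---|
| 4.1 inclusion | before the flip | no pressure criterion |
| 4.2 exclusion | before the flip | ocular surface only |
| 5.5 prior medication | before the flip | no; all permitted |
| Section 6 screening pressure | before the flip | measured, but no limit attached |
| 4.4 withdrawal above 35 mm | after surgery | acts after the dose |
| 8.5 stopping rules | exit or early withdrawal | exit forms only |
| 8.6 medical monitoring | during the study | refers back to the protocol |
| Section 10 weekly monitoring | during the study | no entry role stated |

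No row closes the gap. There is also no exclusion at the investigator's discretion and no clause that adopts the product's labelled contraindications.

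**2. Steroid load.** Topical course: 1 + 1 + 1 = 3 weeks in both groups. The DEXYCU group adds one dose of 517 micrograms.

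**3. Pressure increases expected at the protocol's own rate.** Inputs: 5% to 15% among 339 treated patients (1.6) and 40 subjects (7.1).
- Source data: 339 × 0.05 = 17 and 339 × 0.15 = 51 patients.
- If the coin flip allocates patients, about 40/2 = 20 are treated: 20 × 0.05 = 1 to 20 × 0.15 = 3 cases. Chance of at least one: 1 − 0.95^20 = 0.64 to 1 − 0.85^20 = 0.96.
- If every patient is treated in one eye, which the allocation wording in 3.1 and 5.3 leaves open: 40 × 0.05 = 2 to 40 × 0.15 = 6 cases. Chance of at least one: 1 − 0.95^40 = 0.87 to 1 − 0.85^40 = 0.998.

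These describe DEXYCU patients in general. Section 1.6 gives no rate for vehicle or surgery alone, and none by pressure history.

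**4. Exposure of patients at pressure risk.** Let p be the share of otherwise eligible patients who meet the proposed exclusions. The documents give no value, so p is assumed, from 1% to 20%. The top of the range would suit all pressure disease; the narrower group here should lie lower.

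| p (assumed) | Enrolled, 40p | Expected exposed, patient-level flip, 40p/2 | At least one exposed, 1 − (1 − p/2)^40 | At least one exposed, one eye each, 1 − (1 − p)^40 | Candidates to fill 40 places, 40/(1 − p) |
|---|---|---|---|---|---|
| 1% | 0.4 | 0.2 | 0.18 | 0.33 | 40.4 |
| 5% | 2 | 1 | 0.64 | 0.87 | 42.1 |
| 20% | 8 | 4 | 0.985 | 0.9999 | 50 |

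If each patient is treated in one eye, the expected number exposed is 40p, the second column. The table counts exposure, not harm.

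**The case against.** The case against giving this much weight is fair in several respects.

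- **The documents do not show that these patients fare worse.** Section 1.6 gives one overall band and no rate by pressure history. The higher risk is clinically plausible, but its size is unknown. This stands, and it is why no harm avoided is claimed.
- **Safeguards exist.** Pressure is checked on days 1, 7 and 21, 4.4 describes close postoperative examination, section 10 adds weekly oversight by the investigator, and nothing forbids treating a pressure below 35 mm. The patients come from the investigator's own practice (4.3), and a surgeon is unlikely to operate electively on an eye above 35 mm. All this lowers the risk. None of it is a written rule on who may be randomised.
- **Corneal edema and iritis share the same band in 1.6, so why single out pressure?** Pressure is the one of the three for which the plan already has a screening measurement and a numeric withdrawal limit, so an entry limit follows directly. The other two can reasonably be left to clinical judgement.
- **The product is approved**, as section 11 says. Approval does not settle who should receive added steroid in a trial, and the protocol adopts no label criteria.

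A reader might also infer that all glaucoma, all ocular hypertension and all pressure-lowering treatment must be excluded, and 5.5 rewritten. The documents do not support that. Well-controlled disease is a matter of trade-off in a Phase IV pilot of an approved product, and nothing in the plan shows that such patients cannot safely be included.

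**Conclusion.** The gap is real and should be closed before enrolment. As written, a known steroid pressure responder, or a patient with raised or uncontrolled pressure at screening, can be randomised to added intraocular dexamethasone, and the only pressure limit applies after the dose is in.

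The size can be given only in part. The 1 to 3 or 2 to 6 pressure increases rest on the 1.6 band and on how the coin flip is read. A reader might take them as an excess caused by DEXYCU, or as the number an entry rule would prevent. They are neither, because there is no comparator and no subgroup rate. The number of at-risk patients exposed depends wholly on the assumed p. The conclusion rests on the text of the eligibility and withdrawal rules and does not depend on that assumption.

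Nor does the point show that the trial is unsafe overall. The postoperative checks and the investigator's monitoring limit the risk; they do not control who is randomised.

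**What to change.** Add to 4.2, for either eye and confirmed before the coin flip, exclusion for:

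- (a) a known pressure response to steroid;
- (b) uncontrolled glaucoma or ocular hypertension; or
- (c) a screening pressure above a fixed number well below 35 mm, set in the protocol by the medical expert before enrolment. A value of 25 mm Hg would serve as an example (an assumption; range 21 to 30). It leaves 35 − 25 = 10 mm before the withdrawal limit, or 14 to 5 mm across the range.

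Repeat the criteria in the Study Summary. Excluding well-controlled glaucoma or all pressure-lowering treatment is optional, and 5.5 needs no change.

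**Cost.** One eligibility amendment and no new test, since screening pressure and concomitant medication are already recorded (sections 6 and 9.1). The pool is somewhat smaller: at an assumed p of 1% to 5%, about 40.4 to 42.1 candidates to fill 40 places, and 50 at the unlikely upper value of 20%. Results would apply only to patients without these conditions, which a pilot sized on feasibility can accept.

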4.3 Subject Recruitment and Screening

Subjects will be recruited for the study from principal investigator's clinical practice. As part of the informed consent process, patients will be offered a DEXYCU injection and given a brochure/handout discussing DEXYCU. As part of the standard cataract evaluation process, both tear film osmolarity and corneal staining will be performed.

4.4 Early Withdrawal of Subjects

Subjects will be carefully monitored after surgery, including visual acuity measurements, intraocular pressure measurements, anterior and posterior segment evaluation, as well as dry eye testing. If patients have an intraocular pressure elevation over 35mm that requires additional medication, they will be withdrawn from the study. Also, if patients require a deviation from the standard cataract postoperative regimen, they will be withdrawn from the study.

5 Investigational Product

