5.4 Subject Compliance Monitoring

The study team will assess and track compliance on each study visit (1 day, 1 week, 3 weeks). At all postoperative visits, the study team will monitor adherence to the eyedrop regimen. If there is a significant deviation from the eyedrop regimen, the principal investigator will determine continuation in the study.

A case report binder will be created for each subject in the study. Binder tabs will include:

- Screening Visit
- Day 1 Visit
- Day 7 Visit
- Day 21 Visit
- Exit Form
- Early Exit Visit
- Nonserious Adverse Event Forms
- Serious Adverse Event Forms

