5.6 Packaging, Receiving, Storage, Dispensing and Return

Dexycu will be stored in a locked cabinet. Usage of the medication will be logged.

6 Study Procedures

- Screening Visit
- Day 1 Postoperative Visit
- Day 7 Postoperative Visit
- Day 21 Postoperative Visit

At all visits, visual acuity, eye pressure measurements, tear film osmolarity, and corneal staining will be measured and recorded. At days 7 and 21, patient satisfaction scores will be measured.

7 Statistical Procedures

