7.3 Subject Population(s) for Analysis

All patient who met inclusion criteria and complete the study will be included in the selection of subjects to be included in the analyses.

8 Safety and Adverse Events

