8.1 Definitions

An adverse event is any untoward medical occurrence in a patient who is administered a test article (DEXYCU). The adverse event does not necessarily have a causal relationship with the treatment. An adverse event can therefore be any unfavorable and unintended sign, symptom, or disease temporally associated with the use of the test article, whether or not related to the test article.

A nonserious adverse event is defined as a change in a patient's ophthalmic and or medical health that is not life-threatening, does not require hospitalization, does not prolong a current hospitalization and is not disabling. Nonserious adverse events must be reported by use of a Nonserious Adverse Event Form and may also be reported by a telephone call. All nonserious adverse events must be reported on a Nonserious Adverse Event Form whether they are considered related or unrelated to the test article.

A serious adverse event is defined as any adverse experience occurring at any dose that results in any of the following outcomes: death; a life threatening adverse event, inpatient hospitalization, prolongation of existing hospitalization, or a persistent or significant disability/incapacity.

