8.5 Stopping Rules

Upon completion of the study, an "Exit Form" will be completed and signed by the Principal Investigator. Patients who withdraw early from the study will complete an "Early Exit Visit" form detailing the last visit and reasons for early withdrawal.

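### Section 4.4 ends study participation, not just the protocol regimen, after a treated IOP elevation over 35 mm or a required regimen change, so later safety and dry eye readings are lost

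*Combined protocol and SAP*

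**What the plan says.** Section 4.4 has two mandatory grounds for withdrawal. On pressure: "If patients have an intraocular pressure elevation over 35mm that requires additional medication, they will be withdrawn from the study". On the drops: "if patients require a deviation from the standard cataract postoperative regimen, they will be withdrawn from the study". Both refer to the study, not to the regimen.

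Section 5.2 describes DEXYCU as "administered as a single dose, intraocularly in the posterior chamber at the end of surgery".

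Section 6 lists a screening visit and postoperative visits on Days 1, 7 and 21: "At all visits, visual acuity, eye pressure measurements, tear film osmolarity, and corneal staining will be measured and recorded". Satisfaction is scored on Days 7 and 21. Section 3.2 names osmolarity and corneal staining as primary endpoints and satisfaction as secondary. IOP and visual acuity are not endpoints.

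For patients who leave, section 8.5 says: "Patients who withdraw early from the study will complete an 'Early Exit Visit' form detailing the last visit and reasons for early withdrawal". Section 7.3 defines the analysis population: "All patient who met inclusion criteria and complete the study will be included in the selection of subjects to be included in the analyses".

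Section 8.1 keeps the event on record: "All nonserious adverse events must be reported on a Nonserious Adverse Event Form whether they are considered related or unrelated to the test article". Section 10 provides standard clinical follow-up at 3 months, at 1 year and as clinically needed.

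**The concern.** Withdrawing a patient from a study can protect the patient when it stops a treatment. Here it stops none of the test product, because the only dose has already been given. Pressure medication can be added, or the drops changed, while the patient keeps attending the scheduled visits. What the rule does end is measurement.

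Under the first ground, that ending depends on an outcome: a high, treated pressure is the reason why later study pressures are not taken. Section 1.6 lists raised IOP among the most common reactions to the 517 microgram dose, and both groups also use topical prednisolone for three weeks (3.1). The event may therefore be steroid-related.

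Two things are at stake. The scheduled data would not show the later course of a treated elevation. And because 7.3 keeps only completers, the same patients also drop out of the dry eye comparison, for a reason that may be related to treatment.

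**Working it through.** **Step 1: is there any provision for readings after exit?**

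- Section 6: screening and Days 1, 7 and 21 only.
- Sections 5.4 and 9.2: the binder has an Early Exit Visit tab and adverse event forms, but no tab for a visit after exit.
- Section 8.5: a form on the last visit and the reason for leaving.
- Section 8.6: refers back to the protocol and adds no visit.
- Section 10: clinical follow-up, not described as study measurement.

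No section schedules a study reading after exit. The Early Exit Visit might include one. The case report forms that 9.2 says are included are not in the text available, so this cannot be checked.

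**Step 2: what does one withdrawn patient lose?**

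Inputs from section 6: 3 postoperative visits; 4 measurements per visit (visual acuity, IOP, osmolarity, staining), counted for one eye; satisfaction at 2 visits. Planned total: 3 × 4 = 12 measurements and 2 satisfaction scores. Visits lost = scheduled visits after the exit visit; measurements lost = visits lost × 4.

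| Exit at | Visits lost | Measurements lost | of which IOP | Satisfaction lost |
|---|---|---|---|---|
| Day 1 | 2 of 3 | 2 × 4 = 8 of 12 | 2 | 2 of 2 |
| Day 7 | 1 of 3 | 1 × 4 = 4 of 12 | 1 | 1 of 2 |
| Day 21 | 0 of 3 | 0 of 12 | 0 | 0 of 2 |

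Any reading at an Early Exit Visit would reduce these losses. If the patient stayed on schedule, all the readings counted as lost would be due. Section 3.1 names 1 week and 3 weeks as the postoperative dry eye assessments, so a Day 1 exit loses both.

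**Step 3: what does 7.3 then do?**

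A patient withdrawn on Day 1 or Day 7 has not completed the study, so 7.3 also removes the readings already taken from the analysis. A patient withdrawn on Day 21 has every scheduled reading, yet 7.3 does not say whether that patient counts as a completer.

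**Step 4: how much could the comparison move?**

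The plan gives no rate for either trigger, and its 40 patients rest on feasibility (7.1), so there is no power figure to reproduce. The following is illustration only. Assume 20 patients per group, two-sided alpha 0.05, 80% power, and losses of 1 to 3 in one group.

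- Detectable difference = (1.960 + 0.842) × √(1/20 + 1/n). With n = 20 it is 0.886 SD; with n = 19, 0.898 SD; with n = 17, 0.924 SD.
- Shift of the completer mean = share removed × difference between those removed and those who stay. With 1 of 20 and 0.5 SD: 0.05 × 0.5 = 0.025 SD. With 3 of 20 and 1 SD: 0.15 × 1 = 0.15 SD.

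The cost in precision is small. The problem is that the loss is selective, and its size and direction are unknown.

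**The case against.** The case for leaving 4.4 alone is reasonable in several respects.

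- **Uniform background treatment.** Removing patients whose drops change keeps the regimen the same for a dry eye comparison. That rationale is sound, but a flag and a repeat analysis serve the same purpose without discarding data.
- **The safety loss is thin.** IOP has no planned analysis; 7.2 compares dry eye data only. At most two scheduled IOP readings per eye are lost. At a single centre recruiting from the investigator's own practice, later pressures would probably be in the chart. This narrows the gap but does not close it, since nothing says that those pressures enter the study record. Nor is the loss confined to safety, because the same visits carry both primary endpoints.
- **Few patients may be affected.** This stands: there may be none.

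A reader might also infer more than the documents support:

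- *The event goes unreported, or the patient is abandoned.* No. Section 8.1 requires reporting and sets no cut-off at exit, section 6 records the pressure at the detecting visit, and section 10 continues care.
- *5 to 15% of DEXYCU patients would be withdrawn.* No. That range in 1.6 covers IOP increases of any size; the share over 35 mm needing medication is not given, and neither is the rate of regimen changes.
- *Sections 4.4 and 5.4 conflict.* Section 5.4 says "If there is a significant deviation from the eyedrop regimen, the principal investigator will determine continuation in the study". It concerns adherence to the drops, whereas 4.4 concerns changes that are clinically required. These are different rules for different situations.
- *The result will be biased against or in favour of DEXYCU.* Either group could meet either trigger, and the documents give no direction.

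**Conclusion.** The point holds. Section 4.4 makes leaving the study automatic on both grounds, although withdrawal removes no DEXYCU exposure, and no section schedules readings afterwards. For each affected patient, 2, 1 or 0 of the 3 postoperative visits are lost after a Day 1, Day 7 or Day 21 exit. The losses cover IOP, visual acuity, both primary endpoints and satisfaction, and 7.3 then takes patients who leave before Day 21 out of the analysis altogether.

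This should be changed, but it does not undermine the trial. Confidence is medium. The conclusion rests on the visible text: an Early Exit Visit reading, or an outcome field on the adverse event form, would reduce the safety loss. The counts are for one eye. The 20 per group used for illustration is an assumption, since the randomisation wording in 3.1 and 5.3 leaves it unclear whether patients or eyes are compared.

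**What to change.** - **Section 4.4:** record either situation as a departure from the protocol regimen instead of withdrawal from the study. Treat as clinically needed, keep the patient on the scheduled Day 7 and Day 21 visits, and follow the event to resolution on the adverse event form.
- **Section 8.5:** limit the Early Exit form to patients who decline further visits.
- **Section 7.3:** analyse these patients in the group to which they were randomised, flag readings taken after the regimen change, and repeat the ANOVA without the flagged readings as a sensitivity analysis.

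The cost is amended wording in 4.4 and 8.5 and an added line in 7.3. The visits and measurements are already in section 6, so none is new. The downside is a few more case report pages per affected patient and some dry eye readings taken on changed drops, which the repeat ANOVA covers. The rule for those readings has to be set in advance.
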